7.6.2 Subject Demographics and Baseline Characteristics

Subject demographics of gender and age will be summarized using discrete summary statistics and presented by treatment group. Age will also be summarized using continuous summary statistics. Total ocular surface staining score at baseline will be summarized using continuous summary statistics.

7.6.3 Medical History

Non-ocular and ocular medical history will be summarized using discrete summary statistics and presented by treatment group at the subject and event level by system organ class and preferred term. Ocular medical history will be similarly summarized separately at the subject level for study and fellow eyes separately. If a subject reports the same preferred term multiple times within the same system organ class, then that preferred term will only be reported once within that system organ class. As with the preferred term, if a subject reports multiple conditions within the same system organ class, then that system organ class will only be reported once.

7.6.4 Prior and Concomitant Medications

Ocular and non-ocular prior and concomitant medications will be summarized in separate tables, by Anatomical Therapeutic Classification (ATC) text and preferred term using discrete summary statistics and presented by treatment group. Subjects may have more than one medication per ATC text. At each level of subject summarization, a subject will be counted once if he/she reports one or more medications. Percentages will be based on the number of subjects in each treatment group.

7.6.5 Subject Discontinuation

A disposition of subjects includes the number and percentage of subjects in each of the following categories:

- Subjects in the ITT population
- Subjects in the Safety population
- Subjects in the PP population

For each population, the number and percentage of subjects who completed and discontinued from the study will be summarized using discrete summary statistics and presented by treatment group. The primary reason for study discontinuation described in Section 2.2.3 will also be summarized for each treatment group.

7.6.6 Protocol Deviations

The number of subjects within each type of protocol deviations will be presented using listings and discrete summary statistics as appropriate. Protocol deviations will include, but are not limited to:

- Non-compliance with any scheduled study visit
- Non-compliance with investigational medical device treatment
- Disallowed concomitant medications
- Non-compliance with study inclusion or exclusion criteria
- Non-compliance with study assessment procedures

Deviations with a significant impact on the primary endpoint will be assessed as major deviations.

7.6.7 Treatment Compliance

Subject treatment compliance rate will be calculated by dividing the total frequency of drop instillations recorded in the diary for a subject across the entire treatment period by the total number of days times the expected frequency of drop instillations per day and then multiplying by 100. e.g., ([total frequency of drop instillations recorded in the diary across the entire treatment period] / [(the total number of days of exposure) x (the expected frequency of drop instillations per day)]) x 100.

Overall investigational medical device treatment compliance will be summarized using continuous summary statistics and presented by treatment group. Treatment compliance will also be presented using discrete summary statistics in the following categories: (< 80%, 80-120%, and > 120%). Percentages will be calculated out of the number of subjects who returned diaries from that dosing period. The number and percentage of subjects in each compliance rate category will be presented by treatment group.

7.6.8 Treatment Exposure

Extent of exposure is defined as the total number of days from the first dose date to the last dose date, as recorded at the randomization study visit and the study exit eCRF page. For subjects who are lost to follow-up, extent of exposure will be calculated based on the

last study visit attended. The extent of exposure will be summarized using continuous summary statistics and presented by treatment group.

7.6.9 Missing Data

For subjects who discontinue the study early, analyses of change from baseline to endpoint for continuous variables will be based on the last non-missing post-baseline data (last observation carried forward data imputation methodology).

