2.2.3 Subject Discontinuation

A subject MAY be discontinued (at the discretion of the Investigator, the Sponsor, and/or the EC) prior to the final visit for several reasons, including, but not limited to:

- A serious adverse event (SAE) occurring during the course of the study, which precludes continued treatment or follow-up
- The subject not following required study procedures
- If a subject exhibits intolerable AEs (related or not related to the investigational medical device), or if a subject fails to show improvement or the clinical status worsens, the treating Investigator may opt to withdraw the subject from the study and implement necessary intervention.

A subject MUST be discontinued prior to the final visit for any of the following reasons:

- Voluntary withdrawal
- Death
- Investigator decision that it is not in the best medical interest of the subject to continue participation in the investigation. In case a subject administers more than 8 instillations per day for both eyes on a regularly continued basis (approximately 70 %) as assessed on Visit 4, the subject will be discontinued from the study and the investigator will prescribe an appropriate treatment.

Prior to discontinuing a subject, every effort should be made to contact the subject, schedule a final visit, obtain as much follow-up data as possible, and to retrieve all investigational materials. Adverse events will be followed as described in Section 6.5 . Subject withdrawals will be documented clearly on the source document and applicable electronic case report form (eCRF). The assessments scheduled for Visit 5 should be performed at this early termination visit.

Notification of subject discontinuation will be made to the Sponsor Representative and will be clearly documented on the applicable eCRF. Any subject discontinued from the study will not be replaced.

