7.3 Sample Size

A validated macro SAS v. 9.4 was used for sample size calculation. Assuming a unilateral α risk of 2.5%, a β risk of 10% (90% power), a non-inferiority margin of 2 and a standard deviation of 2.5 on the primary endpoint²², a sample size of 33 evaluable subjects per treatment group is necessary to demonstrate non-inferiority of CBL-102 Eye Drops to Vismed® Multi.

With a projected dropout rate of 10% and a protocol violation rate of 10%, a total of approximately 84 subjects with moderate to severe dry eye will be randomized in this clinical investigation.

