7.4 Randomization

A total of 84 subjects will be randomized to receive CBL-102 Eye Drops or Vismed® Multi in a 1:1 ratio.

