## 7.12 Missing data

For subjects who discontinued the study early, analyses of change from baseline to endpoint for continuous variables will be based on the last non-missing post-baseline data (last observation carried forward data imputation methodology).

For safety data, if the causality assessment of an AE is missing, it will be imputed as “Probably” related to the investigational treatment. Likewise, if the severity is missing, the AE will be assessed as “Severe”.

Regarding diaries, missing data will be discussed during the masked review.

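### Carry-forward enters Day 28 and early-exit exams as Day 90 staining, TFBUT and symptom values; a repeated-measures model with date-based visits is a cheap improvement

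*Protocol*

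**What the plan says.** Protocol 7.6.9 names the "last observation carried forward data imputation methodology" for subjects who leave early. SAP 7.12 repeats the rule: for these subjects, "analyses of change from baseline to endpoint for continuous variables will be based on the last non-missing post-baseline data". Neither section limits how old the carried exam may be. None of the sensitivity analyses in SAP 7.5 and 7.6 deals with missing data.

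Four other parts of the plan determine what gets carried:

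- **Schedule (Protocol Appendix A).** Staining, TFBUT and symptoms are due after baseline only at Visit 4 (Day 28) and Visit 5 (Day 90). The Schirmer test has one post-baseline time (Day 28). So does OSD-QoL (Day 90, or withdrawal).
- **Early exit (Protocol 2.2.3).** "The assessments scheduled for Visit 5 should be performed at this early termination visit". The section also allows withdrawal of a subject who does not improve or gets worse, and requires it for sustained heavy instillation found at Visit 4.
- **Analysis sets (Protocol 7.5, SAP 5).** PP requires staying only through Visit 4. ITT requires a baseline and one later assessment.
- **Model (SAP 7.6).** A separate covariance model is fitted at each post-baseline time. SAS Mixed is named in SAP 7.5, but not for a joint model of the two visits.

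**The concern.** With only two scheduled post-baseline visits, the value carried to Day 90 is either the Day 28 exam or an exam from an early-termination visit. Staying through Visit 4 is enough for PP, so this happens in PP as well as ITT. In ITT, a subject who leaves before Visit 4 with an exit exam contributes that exam as Day 28 too.

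Each carried value is treated as if it had been measured at the labelled time. This is harmless only if scores do not move after the carried exam, or move so that the errors cancel between arms. Because exit may depend on response, neither can be taken for granted. What is at stake is the Day 90 treatment difference for staining, TFBUT and symptoms and, to an extent not quantified here, the supportive ITT analysis at Day 28.

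**Working it through.** **1. The plan's own figures.** Protocol 7.3 uses "a non-inferiority margin of 2 and a standard deviation of 2.5 on the primary endpoint", one-sided alpha 2.5% and 90% power. The true difference is not stated and is taken as 0.

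n per arm = 2 × (1.960 + 1.282)² × 2.5² / 2² = 32.8, rounded up to 33, which agrees with "a sample size of 33 evaluable subjects per treatment group is necessary". Dropout of 10% plus violations of 10% gives 33 / 0.80 = 41.25, so 42 per arm and 84 in total. The plan's figures reproduce, and nothing below changes them.

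**2. How many values are carried.** 10% of 84 is about 8 subjects. The split by arm, and before or after Day 28, is not given.

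**3. First-order bias.** Let p be the proportion leaving after Day 28 and g the mean change from Day 28 to Day 90 (positive = worse), with T for test and C for comparator. If every leaver carries the Day 28 exam:

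bias in (T − C) ≈ −(p_T × g_T − p_C × g_C)

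- A: 10%/10%, both improve 1 grade: −(−0.10 + 0.10) = 0
- B: 10%/10%, T worsens 1, C improves 1: −(0.10 + 0.10) = −0.20
- C: 15%/5%, both improve 1: −(−0.15 + 0.05) = +0.10
- D: 15%/5%, T worsens 3, C worsens 1: −(0.45 − 0.05) = −0.40

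A negative bias favours CBL-102.

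**4. Simulation with exit linked to response.** Each scenario used 3,000 trials of 42 per arm, with SD 2.5 at each visit. Exit after Day 28 was more likely with worse Day 28 staining. Assumed values were baseline SD 1.5, a slope of change on baseline of −0.5 and a Day 28 to Day 90 correlation of 0.5. Carry-forward with ANCOVA was compared with a two-visit mixed model (unstructured covariance, treatment and baseline effects by visit).

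| Scenario | True Day 90 difference | Bias, carry-forward | Bias, mixed model | 95% CI coverage, carry-forward / mixed |
|---|---|---|---|---|
| A | 0 | 0.00 | 0.00 | 94.6% / 94.7% |
| B | 2 | −0.20 | −0.01 | 93.5% / 95.1% |
| C | 0 | +0.16 | −0.02 | 93.2% / 94.2% |
| D | 2 | −0.33 | 0.00 | 90.0% / 94.3% |

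In C and D the simulation lies 0.06 to 0.07 above the first-order figure. Leavers are worse than average at Day 28, carry-forward holds them there, and more of them are in the test arm. With correlation 0.3 or 0.7, scenario D gives −0.29 or −0.35; the mixed model stays at 0.00. Monte Carlo error of a bias is about 0.55 / √3000 = 0.01.

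An observed-case ANCOVA at Day 90 is not a substitute: its bias was −0.12 in C and −0.10 in D.

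**5. Standard errors.** The mean SE was 0.51 to 0.54 for carry-forward and 0.54 to 0.55 for the mixed model. In D, the carry-forward mean SE (0.516) is close to its empirical SD (0.524), so the lost coverage comes mainly from bias.

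**6. Visit labelling.** Early termination uses the Visit 5 assessments, and Protocol 5.1.6 sends out-of-window scheduled visits to the scheduled-visit eCRF. The SAP has no analysis-window rule. An early-exit exam could therefore be stored as Visit 5, and a mixed model would read it as Day 90 as well.

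**The case against.** The strongest reply is that no planned decision depends on this. Non-inferiority is decided in PP at Visit 4, PP members have stayed to that visit, ITT is supportive, and SAP 7.6 labels the secondary tests as informational. The biases rest on assumed dropout splits and trajectories. They vanish with equal dropout and parallel trends, and D is a stress case in which the test arm loses 3 grades after Day 28. All of this stands, and it limits the point to the quality of the Day 90 results.

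The mixed model also has a cost. A subject whose only later exam is an early-exit exam before Day 28 drops out of it. Exit exams outside both visit windows are not used, including those of subjects withdrawn for lack of improvement. That is a reason to keep carry-forward as a sensitivity analysis.

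A reader might infer more than the documents support:

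- **That the non-inferiority conclusion is at risk.** In D the upper limit fell below 2 in 9.5% of runs, against 2.9% for the mixed model. The margin of 2 is defined for Visit 4 only (Protocol 7.2), so this is not an error rate of the trial's test.
- **That everyone leaving after Visit 4 contributes a Day 28 exam.** Where an exit exam is done, that exam is carried. If scores move steadily, the error is then smaller than simulated.
- **That all Day 90 endpoints are affected alike.** OSD-QoL has no Day 28 value to relabel. It and Schirmer gain nothing from a repeated-measures model, and Visit 5 includes no Schirmer test. Missing diary data go to the masked review.
- **That a mixed model cures the problem by itself.** Without a date rule it does not (step 6).

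**Conclusion.** The point holds for total and regional staining, TFBUT and symptom score at Day 90, in ITT and PP, and for early-exit exams used as Day 28 in ITT. For Day 90 staining, the simulated bias is 0 to about 0.2 grade with 10% leaving in each arm and up to about 0.35 grade at 15% versus 5%. Against the planning SD of 2.5 these are at most 0.2 / 2.5 = 0.08 and 0.35 / 2.5 = 0.14 SD. The sign depends on the trend after Day 28; when a difference opens late, carry-forward hides part of it. The mixed model's bias was about 0.02 grade or less, given missing-at-random.

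Only the 10% overall dropout and the SD come from the documents. Arm-specific dropout, trends, correlation and the link between exit and response are assumptions. No figure was derived for TFBUT, symptoms or ITT Day 28. This is a worthwhile improvement to the Day 90 results and does not call the primary conclusion into question.

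**What to change.** Amend SAP 7.6 and 7.12 before the treatment codes are broken:

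1. For Day 90 staining (total and by area), TFBUT and symptom score, replace carry-forward with a mixed model for repeated measures on Day 28 and Day 90. Include treatment, visit, treatment × visit, baseline and baseline × visit, with unstructured covariance, and report the treatment difference at Day 90.
2. Add an analysis-window rule that assigns each exam to a visit by its actual date. An early-termination exam then counts as Day 90 only if it falls in that visit's window. State how late scheduled visits are handled.
3. Keep carry-forward as a sensitivity analysis, including for ITT Day 28, where the mixed model would drop subjects who have only an early-exit exam.
4. Reconcile Protocol 7.6.1, which computes change only when baseline and follow-up are both present, with the imputation in 7.6.9.

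OSD-QoL and Schirmer need no change of model. The cost is SAP wording and modest programming; SAS Mixed is already in use, no new data are needed, and the sample size stays at 84. The downside is reliance on missing-at-random.

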8.0 DATA QUALITY ASSURANCE

8.1 Study Monitoring

The Sponsor Representatives must be allowed to visit all study site locations to assess the data, quality, and study integrity in a manner consistent with applicable health authority regulations and the procedures adopted by the Sponsor Representatives.

Prior to the start of the study the Sponsor Representatives will review the protocol, eCRF, regulatory obligations, and other material or equipment relevant to the conduct of the study with the Investigator/Sub-Investigator and relevant study site personnel.

Monitoring visits and telephone consultations will occur per the monitoring plan during the course of the investigation to verify the following:

- The rights and well-being of subjects are protected
- The conduct of the investigation is in compliance with the currently approved protocol/amendment, ICH GCPs, ISO 14155, and EC requirements
- The integrity of the data, including adequate study documentation
- The facilities remain acceptable
- The Investigator and site personnel remains qualified and able to conduct the study
- Test article accountability

During the course of the study, if the Sponsor determines that an Investigator is non-compliant with the study plan and/or applicable regulatory requirements, the Sponsor, in cooperation with the Sponsor Representatives, will take action to secure compliance. In addition, the Sponsor may terminate the Investigator's participation in the study if appropriate, or if the Investigator remains non-compliant despite the Sponsor's actions.

8.2 Source Documentation

All medical information obtained at each study visit must be recorded in the subject's record (source documentation) in real time as it is collected. Source documentation consists of original subject documents, as well as data and records with information relevant to the subject and his/her participation in the study.

Subject completed forms and diaries are considered source data. Designated site personnel will pre-record appropriate start dates of run-in ART or investigational eye drop administration and subject identifiers (year of birth and/or subject study number) on the diary. With this exception, only subjects are to record information in subject diaries. In no instance, should an Investigator or study site personnel record any data or make

changes to subject completed forms. The Investigator or designee should review diary entries during study visits. If an entry is found to be illegible or a mistake is found (eg, incorrect year was recorded), the subject should be instructed to edit the entry by drawing a single line through the original entry, entering the new information, and adding the date and year of birth next to the change.

8.3 Case Report Forms and Data Verification

Subject data required by this protocol are to be recorded on eCRFs. With the exception of subject diaries, the Investigator and his/her study site personnel will be responsible for completing the eCRFs. The Investigator is required to verify that all of the requested information is accurately recorded on the eCRFs. All information requested on the eCRFs needs to be supplied, including subject identification and date(s), assessment values, etc., and any omission or discrepancy will require explanation. All information on eCRFs must be traceable to source documents. Subject diaries will be handled as described in Section 5.5, Treatment Compliance. Diaries will be sent to Sponsor Representative's Data Management for data capture in the database. A copy of the diary will be left at site as source document.

The study monitor will be responsible for reviewing and verifying the data recorded on the eCRFs, utilizing the original source documentation and will query discrepant findings. The Investigator and study site personnel will be responsible for answering all queries. The eCRFs will be submitted to the Sponsor Representative for quality assurance review, and statistical analysis.

A copy of the eCRFs (on CD or DVD) will be retained by the Investigator, who must ensure that it is stored in a secure place.

8.4 Recording of Data and Retention of Documents

Subject data recorded on eCRFs during the study will be documented in a coded fashion. The subject will only be identified by the subject number and by year of birth, if also required. Confidentiality of subject records must be maintained to ensure adherence to applicable local privacy regulations.

The Investigator must retain essential documents indefinitely after the completion of the study, unless otherwise notified by the Sponsor. The Investigator agrees to adhere to the document retention procedures when signing the protocol Investigator Statement of Approval.

Essential documents include but are not limited to the following:

- EC and /or Competent Authority approvals for the study protocol, all amendments, ICF(s), and advertisements
- EC correspondence and reports (eg, SAE reports, protocol deviations, and safety updates)
- Regulatory documents (eg, financial disclosure and delegation of authority forms)
- All source documents
- eCRFs (on CD or DVD)
- Subject's signed ICF
- Accountability records for the test article(s)

- Correspondence from and to the Sponsor
- Any other documents relevant to the conduct of the study

In the event that the Investigator withdraws from the study (eg, retirement, relocation), study records will be transferred to a mutually agreed upon designee (eg, another Investigator, site IRB/EC). The Investigator will provide notice of such transfer in writing to the Sponsor.

8.5 Auditing Procedures

Audits of clinical research activities may take place. A regulatory authority may also wish to conduct an inspection (during the study or after its completion). If an inspection is requested by a regulatory authority and/or IRB/EC, the Investigator must inform the Sponsor immediately that this request has been made.

8.6 Institutional Review Board/Ethics Committee Approval

The Investigator should ensure that his/her participation in the study, in addition to the protocol, subject recruitment materials (written information or materials including web pages, radio advertisements, television spots or written text developed to encourage subject enrollment) and the ICF to be used in this study are approved by their institution IRB/EC, or if not using their institution's IRB/EC, approved by the reviewing central IRB/EC prior to entering any subjects in the study. Documentation of IRB/EC approval of the study protocol and informed consent must be provided to the Sponsor prior to initiation of the study. In addition, the Investigator must ensure that the reviewing IRB/EC has provided approval for any protocol amendments prior to implementation. If the amendment necessitates a revision to the ICF, the Investigator should ensure the revised form is also submitted to and approved by the Sponsor and the IRB/EC prior to implementation.

8.7 Publication of Results

All study data generated as a result of this study will be regarded as confidential, until appropriate analysis and review by the Sponsor or its designee and the Investigator(s) are completed. The results of the study may be published or presented by the Investigator(s) after the review by, and in consultation and agreement with the Sponsor, and such that confidential or proprietary information is not disclosed.

Prior to publication or presentation, a copy of the final text should be forwarded by the Investigator(s) to the Sponsor or its designee, for comment. Such comments shall aim to ensure the scientific integrity of the proposed publications and/or presentations and ensure that the data and material referring to Bausch & Lomb Incorporated products and activities receive fair, accurate, and reasonable presentation.

